8 MISSING DATA

In the event that a patient withdraws (discontinues the study or is lost to follow-up) from the study, information on their survival and secondary endpoint status at the time they are withdrawn will be included in the relevant endpoint analysis. All available data will be used as appropriate to the objectives and analyses outlined in the analysis plan, there will be no imputation of missing data.

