3.2 Primary Objective

To compare the post-operative incidence of delirium amongst patients undergoing major surgery between those randomised to a BIS of target 50 ('light' anaesthesia) compared with those randomised to a BIS of target 35 ('deep' anaesthesia).

Primary endpoint:

The incidence of post-operative delirium, defined as POD present at any of the 10 assessments over the 5 post-operative days. The 3

minute diagnostic interview for Confusion Assessment Method delirium (3D-CAM) or the CAM-ICU is used to determine the presence of delirium. This will be administered preoperatively and twice daily (05:00 -11:00 and 1800 – 2200) for 5 days postoperatively or until discharge. A modified version will be used for patients in ICU (CAM-ICU) who are unable to talk on these days. Delirium assessment will be performed when patients can be aroused sufficiently in order to be assessed for delirium (Richmond Agitation and Sedation Score >-4).

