4.2 Sample size calculation

Chan *et al.* showed that delirium incidence was reduced from 24.1% to 15.6% with the use of BIS-guided anaesthesia versus routine care in a broadly similar patient group to the BALANCED Study cohort, with the exception that 83% were ASA 1 or 2. Using the data from Chan *et al.* we hypothesise that the incidence of delirium will be reduced from 25% in the deep anaesthesia group (BIS target 35) to 15% in the light anaesthesia group (BIS target 50). A power analysis using this reduction from 25% to 15%, with power of 80% and two-tailed alpha = 0.05, indicates that approximately 270 patients are required in each group (total of 540 patients). We therefore plan to recruit approximately n=600 patients to allow for all-cause loss-to follow-up.

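### Delirium assessments that were missed or could not be done, and deaths before the 3- and 12-month cognitive tests, have no scoring rule and no sensitivity analysis; by default the former count as negative and the latter drop out

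*Combined protocol and SAP*

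**What the plan says.** All references are to the combined protocol and SAP.

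- **Endpoint (section 3.2).** Post-operative delirium is "defined as POD present at any of the 10 assessments over the 5 post-operative days". Assessment is twice daily for five days and ends at discharge if that comes first. It also depends on arousal: "Delirium assessment will be performed when patients can be aroused sufficiently in order to be assessed for delirium", with a sedation score above -4 as the threshold.
- **Analysis set (section 4.3.1).** Every randomised sub-study patient who is induced and has no pre-operative delirium is included. No minimum number of post-operative assessments is required.
- **Primary test (section 7.1).** A Mantel-Haenszel test stratified by centre group, which needs one yes/no value per patient.
- **Missing data (section 8).** For patients who withdraw, meaning they discontinue or are lost to follow-up, "information on their survival and secondary endpoint status at the time they are withdrawn will be included in the relevant endpoint analysis". All available data are to be used and "there will be no imputation of missing data".
- **Late cognition (sections 3.3 and 7.2).** The AMTS is given by telephone at 3 and 12 months. AMTS level is analysed in a linear model with randomised group and centre only. Impairment is compared by a stratified Mantel-Haenszel test.
- **Disposition (section 6).** The flowchart counts patients having each assessment, losses and deaths. It does not say that these counts are by arm, and nothing from it feeds into an analysis.

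**The concern.** An endpoint of the type 'positive at any of up to 10 looks' depends on how many looks each patient had. The plan does not say how a missed or impossible look is scored, what value a patient with no looks receives, or how sensitive the result is to either. The randomised factor is depth of anaesthesia, and whether a patient can be assessed depends partly on arousal, so the chance of detecting delirium could differ between arms. If it did, part of the observed odds ratio would reflect ascertainment and not delirium.

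For late cognition, patients who die before the 3- or 12-month call have no AMTS and no rule. A model of the available scores then describes survivors who could be reached. The pre-operative MMSE is collected (section 5) but is not used as a covariate for the AMTS.

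**Working it through.** **1. The plan's own figure.** Inputs from section 4.2: delirium "reduced from 25% in the deep anaesthesia group (BIS target 35) to 15% in the light anaesthesia group (BIS target 50"), "with power of 80% and two-tailed alpha = 0.05". With mean rate 0.20:

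n = [1.960·√(2·0.20·0.80) + 0.842·√(0.25·0.75 + 0.15·0.85)]² / 0.10² = 250 per group.

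With the continuity correction, n' = (n/4)·[1 + √(1 + 4/(n·0.10))]² = 270 per group. This matches the plan, which "indicates that approximately 270 patients are required in each group (total of 540 patients"). The recruitment target of 600 corresponds to a loss of 1 − 540/600 = 10%, a rate the plan does not state. The sample size is not in error.

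**2. What the rules imply for each type of patient.**

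| Patient | Section 3.2 | Section 4.3.1 | Section 8 | Result |
|---|---|---|---|---|
| Ten negatives | not a case | included | – | non-case |
| Two negatives, eight missed | no positive seen | included | no imputation | non-case by default |
| No assessment | undefined | included | no imputation | no value |
| Death before AMTS | – | included | not covered by the definition of withdrawal | dropped by default |

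The second row is a consequence of the rules taken together; no sentence states it. On the third row the plan pulls two ways: section 4.3.1 keeps the patient, while section 4.2 sizes the trial for losses ("We therefore plan to recruit approximately n=600 patients to allow for all-cause loss-to follow-up").

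**3. Effect of unequal numbers of looks (illustration; the rates are assumptions).** Assume no treatment effect, a 20% risk over 10 looks, a constant hazard per look, and 270 per arm. Then h = 1 − 0.8^0.1 = 0.0221 and P(any positive in k looks) = 1 − (1 − h)^k.

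- k = 9: 0.182; k = 8: 0.163; k = 7: 0.145.
- 8 versus 9 looks: odds ratio 0.88, rejection 8.8% at a nominal 5%.
- 7 versus 9 looks: odds ratio 0.76, rejection 22%.

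Rejection is from a two-sided normal approximation that ignores centre stratification.

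**4. Under-detection when the planned effect is real.** If 10% of cases are missed in the deep arm only, the observed rates are 0.25 × 0.9 = 0.225 and 0.15. The odds ratio (light to deep) moves from 0.53 to 0.61, and power at 270 per arm falls from 83% to 61% (no continuity correction). If the same share is missed in both arms, the odds ratio hardly moves (0.54 at 10%, 0.55 at 20%), but power falls to 78% and 72%.

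**5. Bounds for patients with no outcome.** Suppose 30 of 300 per arm, the implied 10%, have no value and the rest show 25% versus 15% (67.5 and 40.5 expected cases among 270).

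- All missing negative: 0.225 versus 0.135, odds ratio 0.54.
- All missing positive: 0.325 versus 0.235, odds ratio 0.64.
- Missing positive in the deep arm only: 0.325 versus 0.135, odds ratio 0.32.
- Missing positive in the light arm only: 0.225 versus 0.235, odds ratio 1.06.

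**6. Late impairment.** Let loss be l1 among impaired and l0 among other patients, the same in both arms. Each arm's observed odds are the true odds times (1 − l1)/(1 − l0), so the factor cancels. For 10% versus 15% impaired, with l0 = 15% and l1 = 30% or 50%, the odds ratio is 0.630 both before and after loss. The observed prevalence does fall: a true 10% appears as 8.4% or 6.1%.

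**The case against.** The case for the plan has real force.

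- **No sentence scores missed assessments as negative.** Correct. It is the default outcome of the rules, which is why a written rule is needed.
- **Safeguards exist.** Outcome assessors are blinded, the CAM-ICU is provided for ICU patients who cannot talk, and the arousal criterion excludes only sedation scores of -4 or below. Section 6 counts assessments and section 7.2 compares delirium at each one. These reduce the risk of unequal ascertainment, but they do not measure it by arm or test its effect on the primary result.
- **The arm differences are hypothetical.** This stands. The illustrations even need opposite directions: with the ratio taken as light to deep, 0.88 and 0.76 need fewer looks in the light arm, whereas 0.61 needs under-detection in the deep arm.
- **The withdrawal sentence concerns survival and secondary endpoints, and most naturally means that data collected before withdrawal are used.** This stands. A reader might infer that deaths, or lost patients, are carried at their last status. The documents do not support that: withdrawal is defined without death, and no AMTS exists before 3 months to carry. The only earlier post-operative cognitive score is the MMSE, on another scale with another cut-off (below 26, against below 8). The sentence needs clarifying; deleting it would lose the commitment to use withdrawn patients' data.
- **Selective loss need not bias the late comparison.** This stands. A reader might take the fall from 10% to between 8.4% and 6.1% as bias in the treatment effect. It is a single-arm prevalence, and step 6 shows the odds ratio unchanged when the loss mechanism is the same in both arms.

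**Conclusion.** The concern holds as a gap in specification. Partly assessed, all-negative patients are non-cases by default; patients with no assessment are in the analysis set without a value; deaths before the AMTS have no rule; and no missing-data sensitivity analysis is planned. Bias in the primary odds ratio requires in-hospital missed or unrousable assessments to differ by arm. Under the assumed gaps of one or two looks, rejection with no true effect would be about 9% or 22%. These figures rest on a 20% risk, a constant hazard and 270 per arm. The hazard assumption is not suited to days after discharge if those days are in truth delirium-free. The documents do not show that any such difference exists, or which way it would run. The change should be made, but nothing here shows that the primary test or the sample size is wrong.

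**What to change.** **Primary endpoint.** Keep the planned test. State that the endpoint is delirium detected in hospital up to day 5 or discharge, so that ending at discharge is part of the definition. State how partly assessed and unassessed patients are scored. Tabulate assessments completed, missed and not possible because of sedation, by arm. Add a sensitivity analysis that multiply imputes in-hospital missed or unrousable assessments from arm, other assessments, age and pre-operative MMSE, and that includes patients with no assessment. Add best/worst-case bounds as in step 5, because unrousable assessments may not be missing at random.

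**Section 8.** Reword the withdrawal sentence to say that data collected before withdrawal are used and that no status is carried forward to the 3- or 12-month endpoints.

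**Late cognition.** Analyse the 3- and 12-month AMTS jointly in a mixed model with pre-operative MMSE and centre. Report death or impairment as a supportive endpoint, since the mixed model does not itself deal with death.

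**Cost.** An SAP amendment before database lock, which section 9 allows, and modest programming. The imputation assumes missing at random; for the primary endpoint it serves only as a sensitivity analysis. The mixed model makes the same assumption for missing AMTS scores.

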9 PROCEDURE FOR AMENDMENTS TO STATISTICAL PLAN

It is intended that all statistical analyses specified in this protocol will be performed. However, it is conceivable that some scheduled analyses may not be performed. In addition, study observations or analysis results may suggest the need for additional statistical analyses of the collected study data. Any revisions to this document prior to database lock will be made in the form of an amendment to the Statistical Analysis Plan. Any deviations or additional analyses that are performed will be summarised in the form of an addendum to the Statistical Analysis Plan. In either case, deviations (subtractions or additions) from the planned statistical analysis will be fully described in the final clinical study report.
